7.1.3 Baseline and Study Day Definitions

Baseline is defined as the last non-missing measurement taken before study drug vaccination. Where the time is available, the time of the collection must be prior to study drug vaccination. Day 1 observations taken after the vaccination are considered post-baseline values.

Study Day 1 is defined as the date of the vaccination, as recorded on the CRF vaccination page. Other study days are defined relative to the Day 1 (e.g. Day -1 is the day prior to Day 1).

7.1.4 Visit Windows

The End of Treatment visit will be remapped to the next scheduled visit if the day of the visit falls within the protocol scheduled window.

7.2 Analysis Sets

Randomized Set: The Randomized Set will consist of all randomized subjects. Subjects will be summarized according to vaccine received.

Safety Set: The Safety Set will consist of all randomized subjects who received the study vaccine (TDV or HD-TDV). Subjects will be summarized according to vaccine received.

Full Analysis Set (FAS): The FAS will consist of all randomized subjects who received the study vaccine (TDV or HD-TDV) and for whom a valid pre-dose and at least one valid post-dose blood sample are taken. Subjects will be summarized according to vaccine received.

Per-Protocol Set (PPS): The PPS will consist of subjects in the FAS who have no major protocol violations as presented in [Table 7.a](#). The major protocol violation criteria will be defined as part of the blinded data review prior to the unblinding of subject's vaccine assignment. The categories of major protocol violations include: (1) not meeting selected entry criteria, (2) receiving wrong study vaccine except for the packaging issue noted below, (3) receiving prohibited therapies, and (4) other major protocol violations that may be identified during blinded data reviews. Any changes to these criteria after approval of the SAP will be documented and approved in a separate document (blinded data review meeting minutes) prior to database lock and unblinding. Subjects will be summarized according to vaccine received.

Cell-Mediated Immunity Subset (CMI): Cell-mediated immunity will be assessed in a subset of approximately 80 subjects (approximately 40 subjects in each of the IgG positive and negative groups). The CMI subset is a subset of the PPS and will consist of subjects identified at the time of randomization. Subjects will be summarized according to vaccine received.

Background for summarizing data based on the vaccine received instead of randomized vaccine:

This study uses two Dengue vaccine lots (DB0021213 for HD-TDV and DB0040714 for TDV). During the first two packaging campaigns, incorrect vaccine lots were assigned to the two vaccine groups, i.e. DB0021213 as TDV and DB0040714 as HD-TDV. As the labels are blinded, medication identification numbers are used on the vials for identification. Due to this packaging error the medication identification numbers associated with TDV were used on the vials containing HD-TDV and vice versa. Two hundred and fifty subjects had been vaccinated with either TDV or HD-TDV from these two campaigns, and hence these subjects had their vaccine transposed. In this study, subjects are vaccinated only once. The error was identified before the third packaging campaign started, and therefore the only impacted vaccine stock is that from the first and second packaging campaigns.

Due to this packaging issue, the primary analyses of this trial will be based on a PPS that will be adapted in order to exclude all subjects with major protocol violations (as stated above) with the exception that it will include the 250 subjects affected by this packaging issue (provided that there is no other major protocol violation for the subjects). This PPS will analyze the subjects according to the vaccine received. A sensitivity analysis will be performed on the FAS that will also be adapted in order to summarize subjects according to the vaccine received.

This packaging issue is considered to have no impact on the overall distribution of the number of subjects across vaccine groups due to the 1:1 randomization, and for all 250 subjects the vaccine was misallocated 1:1. Furthermore, the study was still ongoing and blinded at the time of these adaptations.

All 250 subjects will be treated as randomization errors within the interactive web response system (IWRS). The deviation will be documented and filed in the Trial Master File. A programming update of the IWRS will be implemented which will flag all 250 subjects with

transposed vaccine groups. This will be visible on the data transfer to ensure correct data in the clinical database/analyses.

7.2.1 Protocol Deviations

The criteria described in [Table 7.a](#) will be used to identify subjects who will be excluded from the PPS and will be identified prior to database lock and unblinding. These criteria are considered to have a potentially significant impact on the immunogenicity, and also vaccine viremia results of the subject. Subjects excluded from PPS due to receiving incorrect vaccine will be identified after unblinding. Reasons for exclusion of subjects from the analysis sets will be summarized based on the Randomized Set.

Table 7.a Criteria for Exclusion from the PPS

Criteria for Exclusion	Probable Method of Identification
Not receiving the study vaccine administration ^(a)	Identified programmatically using “End of Study Drug” page question “Did the subject complete the study vaccine?” and/or dosing data
Not having a valid pre-dose and at least 1 valid post-dose measurement for dengue neutralizing antibodies ^(b)	Identified programmatically using immunogenicity data
Not receiving the assigned vaccine, except for the 250 subjects whose vaccines were transposed because two packaging campaigns assigned incorrect vaccine lots, which was identified on 16Oct2015.	Identified after unblinding (e.g. subject who was randomized to TDV but received HD-TDV, subject who was randomized to HD-TDV but received TDV)
Product preparation error	Identified through protocol deviation log
Subject meets inclusion criterion 5 or any of exclusion criteria 1, 2a, 2c, 2d, 3, 4, 5 or 6 (subject to blinded medical review)	Subjects identified programmatically using CRF-recorded data. Subjects will be identified before unblinding, and a blinded review list sent for clinical science review to determine evaluability status for each identified subject. Note that exclusion criteria 2d and 3 identify subjects’ use of prohibited medications prior to enrollment.
Use of prohibited medications at study start (subject to blinded medical review)	Potential prohibited medications (Appendix C) to be identified by sending a blinded review list of CRF-recorded medication data for medical review to determine evaluability status for each identified subject.

(a) Subjects with this protocol violation will be excluded from the Safety Set, and thus also from the FAS and the PPS.

(b) Subjects with this protocol violation will be excluded from the FAS, and thus also from the PPS.

Measurements for dengue neutralizing antibodies and viremia collected outside the windows as specified below will be excluded from the respective visits in the Per-Protocol analysis:

- Dengue neutralizing antibodies: $D15 \pm 5$ days, $D30 \pm 5$ days, $D90 \pm 15$ days, $D180 \pm 15$ days, $D365 \pm 15$ days
- Viremia: $D5 \pm 1$ day, $D7 \pm 1$ day, $D9 \pm 1$ day, $D11 \pm 1$ day, $D15 \pm 1$ day, $D17 \pm 1$ day, $D21 \pm 2$ days, $D30 \pm 5$ days

Other significant deviations may be identified based on blinded data reviews of deviation logs throughout the study, subject to medical review.

In addition, all significant protocol deviations identified based on the deviation logs will be summarized based on the safety set.

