7.1 Inclusion Criteria

Subject eligibility is determined according to the following criteria:

1. The subject signs and dates a written informed consent form where applicable, and any required privacy authorization prior to the initiation of any trial procedures, after the nature of the trial has been explained according to local regulatory requirements ([Appendix C](#)).
2. The subject is aged 21 to 45 years of age, inclusive.
3. Individuals who are in good health at the time of entry into the trial as determined by medical history, physical examination (including vital signs) and clinical judgment of the Investigator.
4. Individuals who can comply with trial procedures and are available for the duration of follow-up.
5. Subjects have self-declared as never having been vaccinated against Yellow Fever or Japanese Encephalitis Virus.

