9.1.3 Documentation of Trial Entrance/Randomization

Only subjects who have signed the informed consent form, meet all of the inclusion criteria and none of the exclusion criteria are eligible for trial entrance/randomization into the vaccination phase. The list of randomization assignments is produced by IWRS.

If the subject is found to be not eligible for randomization/trial phase, the Investigator should record the primary reason for failure on the screening log.

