13.1.1 Analysis Sets

Safety Set: The Safety Set will consist of all randomized subjects who received the trial vaccine.

Full Analysis Set (FAS): The FAS will consist of all randomized subjects who received the trial vaccination and for whom a valid a pre-dose and at least one valid post-dose blood sample is taken.

Per-Protocol Set (PPS): The PPS will consist of subjects in the FAS who have no major protocol violations. The major protocol violation criteria will be defined as part of the blinded data review prior to the unblinding of subject's treatment assignment. The categories of major protocol violations include: (1) not meeting selected entry criteria, (2) receiving wrong trial treatment (3) receiving prohibited therapies, and (4) other major protocol violations that may be identified during blinded data reviews.

The primary analysis of immunogenicity and vaccine viremia endpoints will be based on the PPS; other supportive analysis may be provided for the FAS. The safety analysis will be based on the Safety Set.

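### The PPS exclusion row in SAP Table 7.a is reversed for inclusion criterion 5: it flags subjects who meet the criterion instead of those who fail it

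*SAP*

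**What the plan says.** SAP 7.2 defines the set by reference to the table: "The PPS will consist of subjects in the FAS who have no major protocol violations as presented in" Table 7.a. The table's first column gives criteria for exclusion, and one row reads "Subject meets inclusion criterion 5 or any of exclusion criteria 1, 2a, 2c, 2d, 3, 4, 5 or 6", followed by a bracketed qualifier that makes it subject to blinded medical review. The second column says that these subjects are found by program from CRF data before unblinding, with "a blinded review list sent for clinical science review to determine evaluability status for each identified subject".

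Inclusion criterion 5 (Protocol 7.1) is: "Subjects have self-declared as never having been vaccinated against Yellow Fever or Japanese Encephalitis Virus". Under Protocol 9.1.3, only consenting subjects who "meet all of the inclusion criteria and none of the exclusion criteria are eligible for trial entrance/randomization".

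Two other places give the direction of the rule. SAP 7.2 says: "The categories of major protocol violations include: (1) not meeting selected entry criteria". Protocol 13.1.1 has the same: "violations include: (1) not meeting selected entry criteria, (2) receiving wrong trial treatment". Neither names the criteria that are selected.

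**The concern.** One verb, *meets*, governs both halves of the row. It is right for the exclusion criteria, where meeting one is the violation. It is wrong for inclusion criterion 5, where meeting it is what the protocol requires for randomization.

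This matters for three reasons.

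- The PPS carries the primary GMT and seropositivity analyses (SAP 7.10.1), the analyses by baseline serostatus (7.10.2), the humoral characterization (7.10.5) and the CMI subset (7.10.6). SAP 7.2.1 itself says that the Table 7.a criteria could have a significant effect on the immunogenicity results.
- Table 7.a is the only place that says which entry criteria count. The general statements in SAP 7.2 and Protocol 13.1.1 show the intended direction but cannot replace the row.
- The row is applied by program, so its wording works as a programming instruction. A programmer who codes the evident intent departs from the approved text, and SAP 7.2 requires changes to these criteria after approval to be documented and approved before database lock and unblinding.

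**Working it through.** No sample-size or power figure bears on this point, and the plan gives no figure to reproduce. The check is a truth table followed by a count.

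**Inputs**
- Planned N = 400 (SAP 4.4).
- I5 = subject meets inclusion criterion 5 (Protocol 7.1).
- E = subject meets at least one exclusion criterion listed in the row.
- v = number of subjects who fail criterion 5. The documents give no value; 0 to 40 is an assumed range for illustration. The counts take E as false for everyone.

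**Rules**
- As written: flag = I5 or E.
- With the direction corrected: flag = (not I5) or E.

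| I5 | E | Flag as written | Flag with direction corrected |
|---|---|---|---|
| yes | yes | yes | yes |
| yes | no | **yes** | **no** |
| no | yes | yes | yes |
| no | no | **no** | **yes** |

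The rules differ only where E is false, and there they are exact opposites. The second line is the ordinary eligible subject. The fourth is the violator whom the row exists to find.

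**Counts.** As written, flagged = 400 − v and not flagged = v. Corrected, flagged = v.

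| v (assumed) | Flagged as written | Violators missed as written | Flagged with direction corrected |
|---|---|---|---|
| 0 | 400 | 0 | 0 |
| 4 | 396 | 4 | 4 |
| 8 | 392 | 8 | 8 |
| 20 | 380 | 20 | 20 |
| 40 | 360 | 40 | 40 |

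**What can repair each error**
- *Eligible subject wrongly listed:* the blinded review decides evaluability for each listed subject, so it can clear this one.
- *Violator not listed:* the review does not see this subject. The prohibited-medication row points to Appendix C, which covers other vaccines only within 14 days (inactivated) or 28 days (live) before Day 1. Exclusion criterion 3 uses the same windows. Criterion 5 has no time limit, so an older vaccination escapes both. What remains is the deviation-log review in SAP 7.2.1, which may identify other significant deviations but does not have to.

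**The self-declaration wording.** Criterion 5 is met by declaring, not by being unvaccinated. A subject who declared no such vaccination and later proves to have had one still literally meets it. The row as written would list that subject, but only among all the eligible ones. A bare reversal of the verb would not list that subject at all. The correction therefore has to name recorded vaccination as well.

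**The case against.** The strongest reply is that this is a slip of wording with safeguards around it. SAP 7.2 and Protocol 13.1.1 state the right direction. A flag leads to a medical review and removes nobody by itself. SAP 7.2 also allows violations identified in blinded data review, and the deviation logs are reviewed. Entry criteria must be confirmed before randomization and Protocol 14.2 allows no exemptions, so a subject who declares such a vaccination should fail screening. A list of all 400 subjects would be noticed at once. The trial is descriptive, the FAS gives a supportive analysis, and no count of violators or programming specification is available to show that any estimate would change.

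Most of this stands, and it limits the consequence. A reader might infer that the row empties the PPS and keeps vaccinated subjects in it. The documents do not support that: the row is subject to review, SAP 7.2 shows the intent, and SAP 7.2 also expects the 250 subjects affected by the packaging error to be in the PPS if they have no other major violation. A reader might also infer that every vaccinated subject escapes the flag; the self-declaration wording shows otherwise. Nor do the readable documents give a reason for criterion 5, so an argument from cross-reactive antibodies would rest on outside knowledge and is not made here.

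The reply does not cure the row. The review acts only on listed subjects, the deviation-log route is discretionary, and no other passage names criterion 5 as a ground for exclusion from the PPS.

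**Conclusion.** Wrong as written. For inclusion criterion 5 the row states the opposite of the rule in SAP 7.2 and Protocol 13.1.1. Taken literally, it lists 400 − v subjects for needless review and misses the v who failed the criterion, assuming 400 subjects and no listed exclusion criterion met. With v = 0 that is 400 of 400 flagged, against none once the direction is corrected. The value of v is unknown and may well be zero, given the screening rules.

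The realistic harm is an uninformative review list and a violator left in the primary-analysis set unless the deviation logs happen to reveal the case. The documents do not show that any GMT or seropositivity estimate would change.

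**What to change.** Reword the start of the Table 7.a row to: *Subject does not meet inclusion criterion 5 (including any recorded prior Yellow Fever or Japanese Encephalitis vaccination despite self-declaration), or meets any of* the exclusion criteria already listed. Keep that list and the bracketed blinded medical review unchanged.

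Before database lock, check that the flagging program uses this direction and also reads recorded vaccination history. Document the change by the route that SAP 7.2 sets out, that is, approved blinded data review minutes before lock and unblinding, or by a SAP amendment.

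The cost is one line of text and one program check. No new data are needed.

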1.3 Protocol Amendment No. 2 Summary of Changes

This document describes the changes in reference to the Protocol incorporating Amendment No. 2.

The primary purpose of this amendment is to remove the planned Day 180 (Month 6) interim analysis and to add to the Day 365 (Month 12) visit the recording of receipt of any licensed dengue vaccine.

The rationale for removing the interim analysis initially planned only to support the planning and execution of other trials in the development plan of TDV is that this is no longer necessary. The rationale for recording at the Day 365 (Month 12) visit the receipt of any licensed dengue vaccine is that a licensed dengue vaccine became available in Singapore during the trial conduct and this information is needed to interpret the immune response data.

Full details of the changes are given below.

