9.1.2 Demographics, Medical History and Prior Medications

Demographic information to be obtained will include date of birth, gender, and race as described by the subject.

Medical History will also be collected, including but not limited to any medical history that may be relevant to subject eligibility for trial participation such as prior vaccinations, concomitant medications, and previous and ongoing illnesses or injuries. Relevant medical history can also include any medical history that contributes to the understanding of an AE that occurs during trial participation, if it represents an exacerbation of an underlying disease/preexisting problem.

All medications (pharmaceutical products only) and vaccines taken or received by the subjects within 4 weeks prior to Day 1 (Month 0), blood products within 3 months prior to Day 1 (Month 0), and immunosuppressive therapy within 6 months prior to Day 1 (Month 0) are to be recorded on the Prior and Concomitant Medications eCRF. The use of antipyretics and/or analgesic medications within 24 hours prior to vaccination must be identified and the reason for their use (prophylaxis versus treatment) must be described in the source documents or the eCRF. Trial vaccination should be delayed if subjects have used antipyretics and/or analgesic medication within 24 hours prior to vaccine administration.

Medications taken for prophylaxis are those intended to prevent the onset of AEs following vaccination. Medications taken for treatment are intended to reduce or eliminate the presence of symptoms that are present.

CONFIDENTIAL

All concomitant therapy taken or received during the period starting with the administration of trial vaccine (Day 1 [Month 0]) and ending one month (minimum of 28 days) after vaccination must be recorded in the subject's source document and eCRF. Additionally, the receipt of any dose of any licensed dengue vaccine should be recorded throughout the trial using the concomitant medication page of the eCRF.

Prohibited Therapies are in Section [7.2](#).

Medical history (including corresponding medication) to be obtained will include any significant conditions or diseases that have disappeared or resolved at or prior to signing of informed consent.

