5.0 ANALYSIS ENDPOINTS

5.1 Primary Endpoints

- Geometric mean titers (GMTs) of neutralizing antibodies for each of the four dengue serotypes post-vaccination on Days 15, 30 (Month 1), 90 (Month 3), 180 (Month 6), 365 (Month 12).
- Seropositivity rates (% of subjects) for each of the four dengue serotypes post-vaccination on Days 15, 30 (Month 1), 90 (Month 3), 180 (Month 6), 365 (Month 12) where seropositivity is defined as a reciprocal neutralizing titer ≥ 10 .

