Appendix C Potential Prohibited Therapies

1. Chronic use of oral steroids (equivalent to 20 mg/day prednisone \geq 12 weeks/ \geq 2 mg/kg body weight/day prednisone \geq 2 weeks) within 60 days prior to Day 1 (Month 0) (use of inhaled, intranasal, or topical corticosteroids is allowed).
2. Receipt of parenteral steroids (equivalent to 20 mg/day prednisone \geq 12 weeks/ \geq 2 mg/kg body weight/day prednisone \geq 2 weeks) within 60 days prior to Day 1 (Month 0).
3. Administration of immunoglobulins and/or any blood products within the 3 months prior to Day 1 (Month 0) or planned administration during the study.
4. Receipt of immunostimulants within 60 days prior to Day 1 (Month 0).
5. Immunosuppressive therapy such as anti-cancer chemotherapy or radiation therapy within 6 months prior to Day 1 (Month 0).
6. Receipt of any other vaccine within 14 days (for inactivated vaccines) or 28 days (for live vaccines) prior to Day 1 (Month 0) or planning to receive any vaccine within 28 days after Day 1 (Month 0).
7. Participation in any clinical study with another investigational product 30 days prior to Day 1 (Month 0) or intent to participate in another clinical study at any time during the conduct of this study.
8. Previous participation in any clinical study of a dengue candidate vaccine, or previous receipt of a dengue vaccine.

Signature Page for DEN-205 Statistical Analysis Plan, Version 2.0, 14 Dec 2017

Title:

Approval	PPD	
----------	-----	--

Approval	PPD	
----------	-----	--

Approval	PPD	
----------	-----	--

Document Number: TAK-003-01091 v2.0

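### The SAP has no rule for neutralizing-antibody titers drawn after a licensed dengue vaccine, although the protocol records receipt in order to interpret the immune data

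*SAP*

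**What the plan says.** Protocol Section 1.3 gives the reason for the new recording: "a licensed dengue vaccine became available in Singapore during the trial conduct and this information is needed to interpret the immune response data". Section 9.1.2 puts it into practice: "the receipt of any dose of any licensed dengue vaccine should be recorded throughout the trial using the concomitant medication page of the eCRF". Section 9.3.4 repeats the instruction for the final visit.

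SAP Section 7.1 says the plan is based on Protocol Version 3.0, which contains this change. The primary endpoints (SAP Section 5.1) are GMTs and seropositivity rates for each serotype at Days 15, 30, 90, 180 and 365. Section 7.10.1 analyzes them on the PPS, with the FAS as support.

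The SAP provisions that bear on the point are these:

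- Table 7.a, medication row: "Use of prohibited medications at study start (subject to blinded medical review", applied through the list in Appendix C.
- Appendix C, item 8: "Previous participation in any clinical study of a dengue candidate vaccine, or previous receipt of a dengue vaccine".
- Section 7.2.1, the only exclusion of single measurements: "Measurements for dengue neutralizing antibodies and viremia collected outside the windows as specified below will be excluded" from the visit concerned in the Per-Protocol analysis.
- Section 7.6: concomitant vaccinations are summarized by vaccine received on the Safety Set. Section 7.1.1 adds listings of all data.

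**The concern.** The late visits describe how long antibody lasts after one dose of the trial vaccine. If a subject takes another dengue vaccine and then gives a Day 365 sample, any boost is counted as persistence after TDV or HD-TDV. The error is upward in each arm, even if uptake is equal between arms.

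The supportive FAS analysis has no rule either, so no planned analysis shows the late titers free of another dengue vaccine. The humoral and CMI summaries (SAP Sections 7.10.5 and 7.10.6) also use the PPS and share the gap. The sponsor has said the information is needed for interpretation, yet the SAP does not say how it will be used.

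**Working it through.** **Step 1. Does any prespecified rule remove a titer drawn after receipt?**

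| Rule | Reach | Removes a post-receipt titer? |
|---|---|---|
| Table 7.a, medication row | Study start | Not for a later dose |
| Table 7.a, exclusion criterion 5; Appendix C item 8 | Dengue vaccine before entry | No |
| Table 7.a, exclusion criterion 3; Appendix C item 6 | Vaccines in the 14 or 28 days before Day 1, or planned within 28 days after | Not for a later dose |
| Section 7.2.1, visit windows | Sample timing only | No |
| Section 7.6 table, Section 7.1.1 listings | Display only | No |
| Section 7.2 and 7.2.1, other violations or deviations found at blinded review | Discretionary, whole subject | Possibly |

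No rule names a licensed dengue vaccine taken during the trial. Footnote (d) of the schedule in SAP Appendix A also omits the sentence on licensed vaccine that footnote (d) of Protocol Table 2.a contains.

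**Step 2. How large could the effect be?**

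The documents give no figure to reproduce: no uptake, fold-rise or SD. The inputs are therefore:

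- n = 200 per arm (Protocol Section 2.0).
- GMT = antilog of the mean log titer (SAP Section 7.10.1).
- Assumed: a share f of an arm receives the licensed vaccine before the sample, and their analyzed titers are R times what they would have been.

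The mean log titer rises by f × log R, so the arm GMT is multiplied by R^f.

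| f (subjects of 200) | R = 2 | R = 4 | R = 10 |
|---|---|---|---|
| 1% (2) | 1.007 | 1.014 | 1.023 |
| 2.5% (5) | 1.018 | 1.035 | 1.059 |
| 5% (10) | 1.035 | 1.072 | 1.122 |
| 10% (20) | 1.072 | 1.149 | 1.259 |

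The seropositivity rate rises by at most f × (1 − p), where p is the rate without the other vaccine. At p = 50% this is 0.5 points for f = 1% and 2.5 points for f = 5%. At p = 90% it is 0.1 and 0.5 points.

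**Step 3. Compare with the precision of the estimate.**

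The 95% CI half-width of an arm GMT is 10^(t × SD/√200), with t = 1.972 on 199 degrees of freedom. For an assumed log10 SD of 0.4 this is 10^0.0558 = 1.14-fold. For 0.8 it is 10^0.1115 = 1.29-fold. The bias is well inside the interval at 1% uptake. It is of similar size only near 10% uptake with a large boost.

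**Step 4. Will receipt be known for everyone?**

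Explicit recording came with the amendment of 25 April 2017. Table 7.a dates the discovery of the packaging error to 16 October 2015. If the 250 affected subjects (250/400 = 62.5%) had been vaccinated by then, their Day 365 window, with its 15 days, closed by about 30 October 2016. That is roughly six months before the amendment. The vaccination dates are an inference, but receipt may be unknown for many subjects.

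**The case against.** The best reply is that the SAP is not silent on evaluability. Section 7.2 leaves the major violation criteria to the blinded data review, lists prohibited therapies without a time limit, adds a category for other violations, and allows documented changes before database lock. Receipt is entered on the concomitant medication page, and Table 7.a sends recorded medications for blinded medical review. A reader might therefore infer too much from saying that post-receipt titers will remain in the analysis. The documents support only that they remain by default. What stands is that this route is discretionary, drops the whole subject with the valid earlier titers, and needs receipt to be classed as a violation. Protocol Section 7.2, where prohibited therapies are defined, names no dengue vaccine taken later than 28 days after Day 1.

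A second reply is that information needed for interpretation need not lead to exclusion. Reporting all titers answers a legitimate question, and the listings show who was vaccinated and when. This is fair, and it is why the FAS should keep every value. But the plan should say which question the primary analysis answers.

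Three further readings are tempting but not supported:

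- **Day 180 is affected.** The documents do not date the licensed vaccine's availability, so exposure at Day 180 cannot be shown or excluded.
- **Unequal uptake biases the comparison of arms.** Chance imbalance between randomized arms is ordinary sampling variation, already reflected in the spread of titers. The SAP plans no GMT ratio.
- **Table 7.a keeps every later user of a prohibited therapy in the PPS.** Some Appendix C items look forward, though they are worded as plans, and the open-ended category in Section 7.2 also applies. The text is ambiguous, and concomitant therapy is routinely recorded for only about 28 days.

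**Conclusion.** The gap is real: the sponsor records receipt in order to interpret the immune data, and the SAP has no rule for using it in the immunogenicity analysis. By default, the primary per-protocol GMTs and seropositivity rates include post-receipt titers, chiefly at Day 365 and at any earlier visit that follows receipt. The bias is upward in each arm, provided that the licensed vaccine raises titers.

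The size is unknown. With an assumed 2- to 10-fold boost, the arm GMT is multiplied by about 1.01 to 1.02 at 1% uptake and 1.04 to 1.12 at 5%. If nobody received the licensed vaccine, there is no effect. All analyses are descriptive, so no test or decision rule is affected. A reader might infer that the primary results are unreliable without a correction. The documents do not support that, because they give no uptake. This is a correction worth making before unblinding, and not one on which the trial's conclusions are shown to depend.

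**What to change.** Add to SAP Section 7.2.1:

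- In the Per-Protocol analysis, MNT, humoral and CMI results from samples taken after a recorded dose of a licensed dengue vaccine are excluded from that sample onward. Results from earlier visits are kept.
- All values stay in the supportive FAS analysis.
- The number of results excluded is tabulated by vaccine received and visit.
- Subjects whose receipt is unknown, for example because they completed before the April 2017 amendment, are retained and counted separately.

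Separately, reconcile the PPS category for prohibited therapies in Section 7.2, which has no time limit, with the restriction to study start in Table 7.a. Note there that concomitant therapy is routinely recorded for only about 28 days after vaccination.

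The cost is some SAP text, one derived flag and one table. Exclusion of single measurements is a tool the SAP already uses for visit windows. The downside is slightly fewer late values in the PPS. The flag will be incomplete where receipt was never asked about, and the separate count makes that visible.
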